#### **8.4.5. Eye Symptom Assessment**

At each study visit, study healthcare providers will evaluate the patient for any symptoms of anterior uveitis as specified in the Schedule of Activities ([Appendix 2](#)). If the patient has no prior ophthalmologist diagnosed anterior uveitis and develops eye pain or discomfort, eye redness, blurring of vision, or any other symptoms suggestive of anterior uveitis, the patient must be evaluated by an ophthalmologist. If a patient has prior history of ophthalmologist diagnosed anterior uveitis, then she/he must be evaluated by a physician for recurrence of anterior uveitis (whenever possible, diagnosis is to be confirmed by an ophthalmologist).

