
Other secondary objectives are:
 
 
To compare both ixekizumab regimens (80 mg Q2W or 80 mg Q4W) to placebo during the 52-week period
 
	
 
Proportion of patients who achieve ASAS20, ASAS40, ASAS5/6, and partial remission by ASAS criteria
 
Change from baseline in the individual components of the ASAS criteria
 
Change from baseline in Bath Ankylosing Spondylitis Disease Activity Index (BASDAI)
 
Proportion of patients reaching BASDAI50
 

Objectives	Endpoints
	
 
• Change from baseline in ASDAS
 
• Proportion of patients who experience clinically-important improvement (change of ASDAS from baseline <math>\geq 1.1</math>), major improvement (change of ASDAS from baseline <math>\geq 2.0</math>), or inactive disease (ASDAS <math>< 1.3</math>), or ASDAS <math>< 2.1</math>
 
• Change from baseline in the measure of C-reactive protein (CRP)
 
• Change from baseline in Bath Ankylosing Spondylitis Functional Index (BASFI)
 
• Change from baseline in mobility                         
 
○ Bath Ankylosing Spondylitis Metrology Index (BASMI) (linear) and individual components
 
○ Chest expansion
 
○ Change from baseline in occiput to wall distance
 
 
 
• Change from baseline in MRI of the SIJ (SPARCC score)
 
• Change from baseline in SPARCC SIJ Structural Score (SSS)
 
• Change from baseline in Maastricht Ankylosing Spondylitis Enthesitis Score (MASES)
 
• Change from baseline in SPARCC Enthesitis Score
 
• The incidence and severity of peripheral arthritis by tender and swollen joint count scores of 46/44 joints
 
• Incidence rate of anterior uveitis or uveitis flares
 
• Change from baseline in the following health outcomes measures: Fatigue numeric rating scale (NRS) score, ASAS Health Index (HI) score, Jenkins Sleep Evaluation Questionnaire (JSEQ), Work Productivity Activity Impairment—Spondyloarthritis (WPAI-SpA) scores, SF-36 (both physical component [PCS] and mental component scores [MCS]), and Quick Inventory of Depressive Symptomatology–Self-Report (16 Items) (QIDS-SR16) score.
 
• Nonsteroidal anti-inflammatory drug (NSAID) intake (ASAS-NSAID score and % of patients taking NSAIDs)
 

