		Proportion of patients with SJC = 0 for patients with current or historical peripheral arthritis at Baseline	Analysis of SJC = 0 only applies to patients with current or historical peripheral arthritis at Baseline	Missing if observed value is missing

Measure	Description	Variable	Derivation / Comment	Imputation Approach if with Missing Components
Anterior Uveitis	At each study visit, study health care providers will evaluate the patient for any symptoms of anterior uveitis.	Incidence and incidence rate of anterior uveitis	Anterior uveitis will be summarized for patients with or without prior anterior uveitis, separately.  Anterior uveitis is identified using the preferred term “iridocyclitis”.	Not applicable (NA)
Non-Steroidal Anti-Inflammatory Drug (NSAID) Intake	Information regarding NSAIDs (including COX-2 inhibitors) intake will be collected in the eCRF and the ASAS-NSAID score will be calculated (Dougados et al. 2011).	Proportion of patients taking NSAID	Proportion of patients taking NSAID (including COX-2 inhibitor) at specified visit	NA
		ASAS - NSAID score	See Section 6.10.4.1 and Appendix 5 for details of deriving ASAS-NSAID score. ASAS-NSAID = 0 if no NSAID use	If NSAID dose is missing, the maximum efficacy dose (Appendix 5) is assumed. If frequency is missing, ‘every day’ intake is assumed. If start/stop dates are missing, follow missing date rule in Section 6.9.2
		ASAS-NSAID score change from baseline	Calculated as: observed ASAS-NSAID score – baseline ASAS-NSAID score	
		ASAS-NSAID50	$100 \times \frac{\text{Baseline ASAS} - \text{NSAID} - \text{Observed ASAS} - \text{NSAID}}{\text{Baseline ASAS} - \text{NSAID}}$ Proportion of patients with at least 50% decrease from baseline in ASAS-NSAID score. Derivation only applies to patients whose ASAS-NSAID is not equal to 0 at baseline.	

Measure	Description	Variable	Derivation / Comment	Imputation Approach if with Missing Components
MRI Sacroiliac Joint (SIJ) (Spondyloarthritis Research Consortium of Canada [SPARCC] Score)	Both left and right SIJ are scored for bone marrow edema. Each side has 6 slices and each slice has 6 scoring units, score of 0 or 1. Total SIJ SPARCC scores can range from 0 to 72 with higher scores reflecting worse disease. Scoring will be performed by a central reader.	SPARCC SIJ Score	The SPARCC SIJ Score is sum of 72 scoring units; the sum ranges from 0 to 72.	See “MRI Data Programming Guidance for AxSpA Studies’ for missing rule and imputation method.

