Measure	Variable	Analysis Method (Sections 6.1 and 6.3)	Population (Section 6.1.1)	Comparison/Time Point	Analysis Type
	TJC = 0 when patients had current or historical peripheral arthritis at baseline (similarly SJC = 0 when patients had current or historical peripheral arthritis at baseline)	Logistic regression analysis with NRI; Fisher’s exact test with NRI	ITT Population with Current or Historical Peripheral Arthritis at Baseline	IXE80Q2W & IXE80Q4W vs. placebo at Week 16 and 52 and all other postbaseline visits in Period 2	Other secondary efficacy analyses (Section 6.10.4).
Anterior uveitis	Crude and exposure-adjusted incidence rates for patients with anterior uveitis	Fisher’s exact test and Poisson regression	ITT Population	IXE80Q2W & IXE80Q4W vs. placebo during Period 2	Other secondary efficacy analyses (Section 6.10.4).
NSAID (including COX-2 inhibitor) Intake	Proportion of patients taking NSAID (including COX-2 inhibitor)	Descriptive statistics	ITT Population	At Baseline (Week 0), Weeks 16, 20, 24, 28, 32, 36, 44, 52.	Analyses on NSAID intake (Section 6.10.4.1)
	Change from baseline in ASAS-NSAID	Descriptive statistics	ITT Population who have NSAID (including COX-2 inhibitor) intake at Baseline	At Weeks 16, 20, 24, 28, 32, 36, 44, 52.	Analyses on NSAID intake (Section 6.10.4.1)

Measure	Variable	Analysis Method (Sections 6.1 and 6.3)	Population (Section 6.1.1)	Comparison/Time Point	Analysis Type
	ASAS-NSAID50	Descriptive statistics	ITT Population who have NSAID (including COX-2 inhibitor) intake at Baseline	At Weeks 16, 20, 24, 28, 32, 36, 44, 52.	Analyses on NSAID intake (Section 6.10.4.1)

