#### **6.10.4. Other Secondary Efficacy Analyses**

There will be no adjustment for multiple comparisons for other secondary efficacy analyses.

The other secondary efficacy analyses include:

- ASAS40: analyses other than primary analysis (Section 6.10.1), and additional analysis of the primary outcome (Section 6.10.3)
- ASAS20, ASAS5/6 and partial remission
- Change from baseline in individual components of the ASAS criteria (patient global, spinal pain, function [see BASFI below], inflammation [see BASDAI below], CRP [see CRP below], and spinal mobility (lateral spinal flexion) [see BASMI below])
- Change from baseline in BASDAI: analyses other than major secondary efficacy analysis, 6 individual items and inflammation (mean of Q5 and Q6 on BASDAI)
- BASDAI 50
- Change from baseline in ASDAS: analyses other than major secondary efficacy analysis (Section 6.10.2)
- ASDAS inactive disease (ASDAS<1.3)
- ASDAS disease activity states: inactive disease, low disease activity, high disease activity, very high disease activity, clinically important improvement and major improvement
- Change from baseline in CRP
- Change from baseline in BASFI
- Change from baseline in mobility (BASMI linear and individual components, chest expansion, occiput to wall distance)
- Change from baseline in SPARCC SIJ score: analyses other than major secondary efficacy analysis (Section 6.10.2)
- Change from baseline in SPARCC SIJ structural score (SSS) for each of the 4 features: fat metaplasia, bone erosion, backfill and ankyloses.

- Change from baseline in enthesitis score (MASES and SPARCC)
- Change from baseline in TJC and SJC scores
- Incidence of peripheral arthritis by TJC and SJC scores of 46/44 joints.
- Incidence rate of anterior uveitis
- Change from baseline in ASAS-NSAID score, Section [6.10.4.1](#).

Treatment comparisons of each ixekizumab treatment group and placebo at Weeks 16 and 52 and all other postbaseline visits during Period 2 for the ITT Population will be provided. For inadequate responders who were treated with biologic rescue of ixekizumab 80 mg Q2W, only data up to the time of initiation of biologic rescue of ixekizumab 80 mg Q2W will be included in these analysis.

The impact of ixekizumab starting doses will be evaluated for the selected categorical responses and mean change in selected continuous efficacy and health outcome measures at Weeks 16 and 52 and earlier time point as described in Section [6.1.2](#).

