In general, for all AE-related summaries, the number and percentage of patients experiencing the events will be presented by treatment group. In general, events will be ordered by decreasing frequency in the total ixekizumab group, followed in the order of ixekizumab Q2W, ixekizumab Q4W, and placebo (when applicable) group, within SOC and/or PT for sorting. For events that are gender-specific (as defined by MedDRA), the denominator and computation of the percentage will include only patients from the given gender.

The exposure-adjusted incidence rates (that is, person-time-adjusted incidence rates) over the entire time period for overall summary of AEs and TEAE by maximum severity, SOC, and PT will also be summarized for the following populations:

- Safety Population in Period 2 prior to initiation of biologic rescue of ixekizumab 80 mg Q2W
- Inadequate Response Population in Period 2 post initiation of biologic rescue of ixekizumab 80 mg Q2W

Summary tables comparing exposure-adjusted incidence rates will be generated for patients with AEs and TEAEs where total number of patients experienced the TEAE will be divided by the sum of all patients' time (in 100 years) of exposure during the above mentioned treatment period. Tables will include the total number of patients in each treatment group, the total person years, and the incidence rate ((number of patients with the event / total person years)\*100). The relative risk and p-value will be produced for the Safety population in Period 2 prior to initiation

of biologic rescue of ixekizumab and will be derived from a Poisson regression model with treatment as explanatory variable. The p-value will be based on the likelihood ratio test.

A by-patient listing of all AEs will be provided.

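### The uveitis endpoint covers anterior uveitis or flares, but the SAP counts it through one preferred term and, on its natural reading, once per patient, so the rate can be understated

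*SAP*

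**What the plan says.** Protocol Table RHBX.1 and SAP Section 4 both list, among the other secondary endpoints, "Incidence rate of anterior uveitis or uveitis flares".

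SAP Table RHBX.6.4 names the variable as the incidence and incidence rate of anterior uveitis alone. It gives one identification rule, "Anterior uveitis is identified using the preferred term “iridocyclitis", and one presentation rule: "Anterior uveitis will be summarized for patients with or without prior anterior uveitis, separately". SAP Section 6.10.4 lists the analysis as "Incidence rate of anterior uveitis", without flares.

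SAP Table RHBX.6.5 gives the analysed variable as "Crude and exposure-adjusted incidence rates for patients with anterior uveitis" and the method as "Fisher’s exact test and Poisson regression", comparing each ixekizumab regimen with placebo during Period 2.

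On ascertainment, Protocol Section 8.4.5 has eye symptoms checked at each visit. For a patient whose anterior uveitis was previously diagnosed by an ophthalmologist, "then she/he must be evaluated by a physician for recurrence of anterior uveitis".

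**The concern.** The endpoint has two parts, anterior uveitis and flares of uveitis. The derivation keeps the first and gives no rule for the second. Adverse events are coded in MedDRA (SAP Section 6.13.2), so the choice of preferred terms decides what enters the count, and one term is a hard filter. An event coded elsewhere contributes nothing, and the uveitis row provides no medical review or fallback. The documents themselves use the unqualified word, in the endpoint, in the history-of-uveitis subgroup (SAP Section 6.15.1) and in the heading of the spondyloarthritis feature (Protocol Appendix 5), so a site entry of plain uveitis is foreseeable.

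The second issue is the unit of counting. Patients with prior disease are examined for recurrence, but the analysed variable counts patients. What is at stake is whether the reported figure is the rate that the endpoint promises.

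**Working it through.** The documents give no expected uveitis rate, event count or power for this endpoint, so there is no planned figure to reproduce. The check is first a comparison of text, then an illustration with assumed inputs.

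**Text**

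1. *Scope.* Protocol Table RHBX.1 and SAP Section 4: anterior uveitis or uveitis flares. SAP Table RHBX.6.4 and Section 6.10.4: anterior uveitis. The SAP therefore disagrees with itself as well as with the protocol.
2. *Terms.* Table RHBX.6.4 uses one preferred term. The SAP appendices are blacked out, but this row cites none, whereas the joint-count and NSAID rows do. Table RHBX.6.8 has no uveitis topic. Elsewhere the SAP is broader: Section 6.13.3.1 identifies special topics by standardised queries or term listings, inflammatory bowel disease uses several terms plus a broad list, and broad opportunistic-infection terms go to medical review.
3. *Unit.* Table RHBX.6.5 refers to patients with the event, and Fisher's exact test works per patient. The only formula in the SAP for an exposure-adjusted incidence rate, in Section 6.13.2, has this ratio: "number of patients with the event / total person years". On that reading second and later episodes add nothing. The uveitis row has no formula of its own.
4. *Episodes.* No readable text defines a flare or the gap between two episodes.

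**Illustration**

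Let *s* be the share of affected patients whose events are coded only to other terms, and *m* the mean number of flares per affected patient. Both are assumptions. With *N* affected patients, the plan counts *N*(1 − *s*) and the number of flares is *Nm*, so the share captured is (1 − *s*)/*m*. Take an assumed true first-event rate of 5 per 100 patient-years:

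| *s* | *m* | Share captured | Planned rate, 5(1 − *s*) | Flare rate, 5*m* |
|---|---|---|---|---|
| 0 | 1 | 100% | 5.0 | 5.0 |
| 0 | 1.25 | 80% | 5.0 | 6.25 |
| 0.25 | 1 | 75% | 3.75 | 5.0 |
| 0.25 | 1.25 | 60% | 3.75 | 6.25 |
| 0.5 | 2 | 25% | 2.5 | 10.0 |

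With about 100 patients per arm (SAP Section 5.2), each patient missed is about 1 percentage point of crude incidence.

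**The case against.** The strongest reply is that nobody can tell from these documents whether any event would be lost. They do not show how a site's wording is coded, and reports of anterior uveitis may well all reach the chosen term. A single specific term also protects against counting non-anterior disease. An event coded elsewhere would still appear in the summary by preferred term and in the by-patient listing of all adverse events (SAP Section 6.13.2). All of this stands, and it limits the point to what the rule excludes, not how many events it excludes. It does not remove the mismatch, because those other outputs do not estimate the endpoint.

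A reader might infer more than the text supports:

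- *That flares are not measured at all.* A first on-study flare in a patient with prior uveitis is counted, if coded to the term, in the with-history summary. The gap concerns second and later episodes.
- *That repeat flares can never be counted.* The per-patient reading is the natural one, but it relies on the wording of Table RHBX.6.5 and on a formula from the adverse-event section. Poisson regression could take event counts.
- *That loss is greater in patients with prior uveitis.* Protocol Section 8.4.5 lets a physician evaluate them, with ophthalmologist confirmation where feasible. But these patients already carry a specific diagnosis and are checked for its recurrence, which could equally favour the specific term. Nor does Table RHBX.6.5 plan a comparison of the two history groups.
- *That a difference between arms could be removed or reversed.* Nothing in this blinded trial suggests that coding would differ by arm. With few events there may also be no significant difference to lose: 4/100 against 0/100 gives a two-sided Fisher p of 2 × (100·99·98·97)/(200·199·198·197) = 0.12.

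**Conclusion.** The point holds as a mismatch between a stated endpoint and its derivation. Two exclusions follow from the SAP as written. Events coded to another uveitis-type term are certainly outside the count. Second and later flares in the same patient are outside it on the most natural reading. The rate can therefore be understated; that it is understated is not shown. The 25% to 100% range in the illustration rests wholly on the assumed *s* (0 to 0.5) and *m* (1 to 2) and is not an estimate for this trial.

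Severity is minor. This is one of many other secondary endpoints, SAP Section 6.10.4 applies no multiplicity adjustment to them, and no primary or major secondary conclusion depends on it.

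**What to change.** Before unblinding, amend the uveitis row of SAP Table RHBX.6.4:

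- Replace the single term with a prespecified list of uveitis-type preferred terms from the MedDRA version in use, with blinded medical review to classify nonspecific terms as anterior or not.
- Define a flare as a new episode starting after first dose, and state the gap that separates two episodes. Tying the definition to the start date matters because the treatment-emergent rule in SAP Section 6.13.2, if applied here, could drop a flare no more severe than a pre-existing condition recorded under the same lowest level term.
- Keep the planned per-patient incidence. Add flares per 100 patient-years by arm and by prior-uveitis history, using a method that allows for repeat events within a patient, such as Poisson regression with a robust variance.
- State in Table RHBX.6.5 whether each rate counts patients or episodes, and align SAP Section 4, both tables and Section 6.10.4.

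The cost is SAP text, blinded review of what should be a small number of events already in the database, and possibly a site query where a report is nonspecific. No new study procedure is needed.

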**Table RHBX.6.5. Description of Primary and Secondary Efficacy Analyses**

Measure	Variable	Analysis Method (Sections 6.1 and 6.3)	Population (Section 6.1.1)	Comparison/Time Point	Analysis Type
ASAS40	ASAS40 – Primary	Logistic regression analysis with NRI	ITT Population	IXE80Q2W & IXE80Q4W vs. placebo at Week 16	Primary analysis is logistic regression analysis with NRI for ITT Population comparing IXE80Q2W & IXE80Q4W vs. placebo at Week 16 (Section 6.10.1).
		Logistic regression analysis with NRI	ITT Population	IXE80Q2W & IXE80Q4W vs. placebo at Week 52	Primary analysis is logistic regression analysis with NRI for ITT Population comparing IXE80Q2W & IXE80Q4W vs. placebo at Week 52 (Section 6.10.1).
		Logistic regression analysis with NRI	ITT Population	IXE80Q2W & IXE80Q4W vs. placebo at all other postbaseline visits in Period 2	Additional analyses of primary outcome (Section 6.10.3).
		Logistic regression analysis with NRI	Per-Protocol Set (PPS)	IXE80Q2W & IXE80Q4W vs. placebo at Weeks 16 and 52	Additional analyses of primary outcome (Section 6.10.3).
		Categorical MMRM	ITT Population	IXE80Q2W & IXE80Q4W vs. placebo at Weeks 16 and 52 and all other postbaseline visits in Period 2	Additional analysis of primary outcome (Section 6.10.3).
		Fisher’s exact test with NRI	ITT Population	IXE80Q2W & IXE80Q4W vs. placebo at Weeks 16 and 52 and all other postbaseline visits in Period 2	Additional analyses of primary outcome (Section 6.10.3).
		Logistic regression analysis with NRI	ITT Population	IXE80Q2W & IXE80Q4W Starting Dose 160 mg and 80 mg during Period 2	Other secondary efficacy analyses for primary outcome (Section 6.10.4).
		pMI	ITT Population	IXE80Q2W & IXE80Q4W vs. placebo at Weeks 16 and 52	Sensitivity analyses (Section 6.10.5.1)
		Tipping point analysis	ITT Population	IXE80Q2W & IXE80Q4W vs. placebo at Weeks 16 and 52	Sensitivity analyses (Section 6.10.5.2)
		Subgroup analyses	ITT Population	IXE80Q2W & IXE80Q4W vs. placebo at Weeks 16 and 52	Subgroup analyses (Section 6.15.1)

Measure	Variable	Analysis Method (Sections 6.1 and 6.3)	Population (Section 6.1.1)	Comparison/Time Point	Analysis Type
		Descriptive statistics of ASAS40 response rate	IR Population	Period 2 post initiation of biologic rescue of ixekizumab 80 mg Q2W	Exploratory analyses (Section 6.10.6.1)
ASAS20	ASAS20	Logistic regression analysis with NRI	ITT Population	IXE80Q2W & IXE80Q4W vs. placebo at Weeks 16 and 52 as well as all other postbaseline visits in Period 2	Other secondary efficacy analyses (Section 6.10.4).
		Fisher’s exact test with NRI	ITT Population	IXE80Q2W & IXE80Q4W vs. placebo at Weeks 16 and W52 and all other postbaseline visits in Period 2	Other secondary efficacy analyses (Section 6.10.4).
		Logistic regression analysis with NRI	ITT Population	IXE80Q2W & IXE80Q4W Starting Dose 160 mg and 80 mg during Period 2	Other secondary efficacy analyses (Section 6.10.4).
		Descriptive statistics of ASAS20 response rate	IR Population	Period 2 post initiation of biologic rescue of ixekizumab 80 mg Q2W	Exploratory analyses (Section 6.10.6.1)
ASDAS	ASDAS crp change – Major Secondary	MMRM	ITT Population	IXE80Q2W & IXE80Q4W vs. placebo at Weeks 16 and 52	Major secondary efficacy analysis is MMRM analysis for ITT Population comparing IXE80Q2W & IXE80Q4W vs. placebo at Weeks 16 and 52 (Section 6.10.2).
		MMRM	ITT Population	IXE80Q2W & IXE80Q4W vs. placebo at all other postbaseline visits in Period 2	Other secondary efficacy analyses (Section 6.10.4).
		ANCOVA with mBOCF	ITT Population	IXE80Q2W & IXE80Q4W vs. placebo at Weeks 16 and 52 and all other postbaseline visits in Period 2	Other secondary efficacy analyses (Section 6.10.4).
		pMI	ITT Population	IXE80Q2W & IXE80Q4W vs. placebo at Weeks 16 and 52	Sensitivity analyses (Section 6.10.5.1)
		Tipping point analysis	ITT Population	IXE80Q2W & IXE80Q4W vs. placebo at Weeks 16 and 52	Sensitivity analyses (Section 6.10.5.2)

Measure	Variable	Analysis Method (Sections 6.1 and 6.3)	Population (Section 6.1.1)	Comparison/Time Point	Analysis Type
ASDAS	ASDAS <2.1 (Major Secondary endpoint – ASDAS <2.1)  ASDAS Inactive Disease	Logistic regression analysis with NRI	ITT population with baseline ASDAS $\geq$ 2.1 for ASDAS <2.1  ITT Population for ASDAS inactive disease;	IXE80Q2W & IXE80Q4W vs. placebo at Weeks 16 and 52	.Major secondary efficacy analysis is logistic regression analysis with NRI for ITT Population comparing IXE80Q2W & IXE80Q4W vs. placebo at Weeks 16 and 52 (Section 6.10.2) for ASDAS <2.1.  Other secondary efficacy analyses (Section 6.10.4) for ASDAS inactive disease.
		Logistic regression analysis with NRI	ITT Population	IXE80Q2W & IXE80Q4W vs. placebo at all other postbaseline visits in Period 2	Other secondary efficacy analyses (Section 6.10.4).
		Categorical MMRM (for ASDAS <2.1 only)	ITT Population	IXE80Q2W & IXE80Q4W vs. placebo at Weeks 16 and 52 and all other postbaseline visits in Period 2	Other secondary efficacy analyses (Section 6.10.4).
		Fisher’s exact test with NRI	ITT Population	IXE80Q2W & IXE80Q4W vs. placebo at Weeks 16 and 52 and all other postbaseline visits in Period 2	Other secondary efficacy analyses (Section 6.10.4).
		Logistic regression analysis with NRI (for ASDAS <2.1 only)	ITT Population	IXE80Q2W & IXE80Q4W Starting Dose 160 mg and 80 mg during Period 2	Other secondary efficacy analyses (Section 6.10.4).
		Subgroup analyses (for ASDAS <2.1 only)	ITT Population	IXE80Q2W & IXE80Q4W vs. placebo at Weeks 16 and 52	Subgroup analysis (Section 6.15.1)
		Descriptive statistics of ASDAS <2.1	IR Population	Period 2 post initiation of biologic rescue of ixekizumab 80 mg Q2W	Exploratory analyses (Section 6.10.6.1)
ASDAS	ASDAS Disease Activity States	Repeated measures proportional odds model analysis with NRI	ITT Population	IXE80Q2W & IXE80Q4W vs. placebo at all other postbaseline visits in Period 2	Other secondary efficacy analyses for primary outcome (Section 6.10.4)

Measure	Variable	Analysis Method (Sections 6.1 and 6.3)	Population (Section 6.1.1)	Comparison/Time Point	Analysis Type
ASDAS	ASDAS clinical important improvement; major improvement	Logistic regression analysis with NRI; Fisher's exact test with NRI	ITT Population	IXE80Q2W & IXE80Q4W vs. placebo at Weeks 16 and 52 and all other postbaseline visits in Period 2	Other secondary efficacy analyses (Section 6.10.4).
		Logistic regression analysis with NRI	ITT Population	IXE80Q2W & IXE80Q4W Starting Dose 160 mg and 80 mg during Period 2	Other secondary efficacy analyses (Section 6.10.4).
		Descriptive statistics of response rate	IR Population	Period 2 post initiation of biologic rescue of ixekizumab 80 mg Q2W	Exploratory analyses (Section 6.10.6.1)
BASDAI	BASDAI50	Logistic regression analysis with NRI	ITT Population	IXE80Q2W & IXE80Q4W vs. placebo at Weeks 16 and 52 and all other postbaseline visits in Period 2	Other secondary efficacy analyses (Section 6.10.4).
		Fisher's exact test with NRI	ITT Population	IXE80Q2W & IXE80Q4W vs. placebo at Weeks 16 and 52 and all other postbaseline visits in Period 2	Other secondary efficacy analyses (Section 6.10.4).
		Descriptive statistics of BASDAI50 response rate	IR Population	Period 2 post initiation of biologic rescue of ixekizumab 80 mg Q2W	Exploratory analyses (Section 6.10.6.1)
BASDAI	BASDAI change (Major Secondary) and % improvement from baseline (incl. 6 individual item and inflammation)	MMRM	ITT Population	IXE80Q2W & IXE80Q4W vs. placebo at Weeks 16 and 52 and all other postbaseline visits in Period 2	Major secondary efficacy analysis is MMRM mean change analysis for ITT Population comparing IXE80Q2W & IXE80Q4W vs. placebo at Weeks 16 and 52 (Section 6.10.2).
		ANCOVA with mBOCF	ITT Population	IXE80Q2W & IXE80Q4W vs. placebo at Weeks 16 and 52 and all other postbaseline visits in Period 2	Other secondary efficacy analyses (Section 6.10.4).
		Descriptive statistics	IR Population	Period 2 post initiation of biologic rescue of ixekizumab 80 mg Q2W	Exploratory analyses (Section 6.10.6.1)
BASFI	BASFI change from baseline and % improvement	MMRM	ITT Population	IXE80Q2W & IXE80Q4W vs. placebo at Weeks 16 and 52	Other secondary efficacy analyses (Section 6.10.4).
		MMRM	ITT Population	IXE80Q2W & IXE80Q4W vs. placebo at all other postbaseline visits in Period 2	Other secondary efficacy analyses (Section 6.10.4).

Measure	Variable	Analysis Method (Sections 6.1 and 6.3)	Population (Section 6.1.1)	Comparison/Time Point	Analysis Type
	from baseline	ANCOVA with mBOCF	ITT Population	IXE80Q2W & IXE80Q4W vs. placebo at Weeks 16 and 52 and all other postbaseline visits in Period 2	Other secondary efficacy analyses (Section 6.10.4).
		MMRM	ITT Population	IXE80Q2W & IXE80Q4W Starting Dose 160 mg and 80 mg during Period 2	Other secondary efficacy analyses (Section 6.10.4).
		Descriptive statistics	IR Population	Period 2 post initiation of biologic rescue of ixekizumab 80 mg Q2W	Exploratory analyses (Section 6.10.6.1)
SPARCC SIJ Score	SPARCC SIJ score change from baseline (major secondary)	ANCOVA with observed case analysis	ITT Population	IXE80Q2W & IXE80Q4W vs. placebo at Week 16	Major secondary efficacy analyses (Section 6.10.4).
		ANCOVA with observed case analysis	ITT Population	IXE80Q2W & IXE80Q4W vs. placebo at Week 52	Other secondary efficacy analyses (Section 6.10.4).
		ANCOVA with mBOCF	ITT Population	IXE80Q2W & IXE80Q4W vs. placebo at Weeks 16 and 52	Other secondary efficacy analyses (Section 6.10.4).
SPARCC SIJ Structural Score (SSS)	SPARCC SIJ SSS score change from baseline for each of the 4 features: fat metaplasia, bone erosion, backfill and anklyosis	ANCOVA with observed case analysis	ITT Population	IXE80Q2W & IXE80Q4W vs. placebo at Weeks 16 and 52	Other secondary efficacy analyses (Section 6.10.4).
		ANCOVA with mBOCF	ITT Population	IXE80Q2W & IXE80Q4W vs. placebo at Weeks 16 and 52	Other secondary efficacy analyses (Section 6.10.4).
ASAS	ASAS5/6 and ASAS partial remission	Logistic regression analysis with NRI; Fisher's exact test with NRI	ITT Population	IXE80Q2W & IXE80Q4W vs. placebo at Weeks 16 and 52 and all other postbaseline visits in Period 2	Other secondary efficacy analyses (Section 6.10.4).
Patient Global	Patient Global change and % improvement from baseline	MMRM	ITT Population	IXE80Q2W & IXE80Q4W vs. placebo at Weeks 16 and 52 and all other postbaseline visits in Period 2	Other secondary efficacy analyses (Section 6.10.4).
		ANCOVA with mBOCF	ITT Population	IXE80Q2W & IXE80Q4W vs. placebo at Weeks 16 and 52 and all other postbaseline visits in Period 2	Other secondary efficacy analyses (Section 6.10.4).

Measure	Variable	Analysis Method (Sections 6.1 and 6.3)	Population (Section 6.1.1)	Comparison/Time Point	Analysis Type
Spinal Pain	Spinal Pain and Spinal Pain at night change and % improvement from baseline	MMRM	ITT Population	IXE80Q2W & IXE80Q4W vs. placebo at Weeks 16 and 52 and all other postbaseline visits in Period 2	Other secondary efficacy analyses (Section 6.10.4).
		ANCOVA with mBOCF	ITT Population	IXE80Q2W & IXE80Q4W vs. placebo at Weeks 16 and 52 and all other postbaseline visits in Period 2	Other secondary efficacy analyses (Section 6.10.4).
CRP	CRP change from baseline; ratio of postbaseline to baseline CRP	MMRM	ITT Population	IXE80Q2W & IXE80Q4W vs. placebo at Weeks 16 and 52 and all other postbaseline visits in Period 2	Other secondary efficacy analyses (Section 6.10.4).
		ANCOVA with mBOCF	ITT Population	IXE80Q2W & IXE80Q4W vs. placebo at Weeks 16 and 52 and all other postbaseline visits in Period 2	Other secondary efficacy analyses (Section 6.10.4).
		MMRM	ITT Population	IXE80Q2W & IXE80Q4W Starting Dose 160 mg and 80 mg during Period 2	Other secondary efficacy analyses (Section 6.10.4).
Mobility related measures	BASMI linear (incl. 5 components); chest expansion, occiput to wall distance change from baseline	MMRM	ITT Population	IXE80Q2W & IXE80Q4W vs. placebo at Weeks 16 and 52 and all other postbaseline visits in Period 2	Other secondary efficacy analyses (Section 6.10.4).
		ANCOVA with mBOCF	ITT Population	IXE80Q2W & IXE80Q4W vs. placebo at Weeks 16 and 52 and all other postbaseline visits in Period 2	Other secondary efficacy analyses (Section 6.10.4).
Enthesitis Scores	MASSES and SPARCC change from baseline	MMRM	ITT Population with Baseline MASSES >0 (or SPARCC >0)	IXE80Q2W & IXE80Q4W vs. placebo at Weeks 16 and 52 and all other postbaseline visits in Period 2	Other secondary efficacy analyses (Section 6.10.4).
		ANCOVA with mBOCF	ITT Population with Baseline MASSES >0 (or SPARCC >0)	IXE80Q2W & IXE80Q4W vs. placebo at Weeks 16 and 52 and all other postbaseline visits in Period 2	Other secondary efficacy analyses (Section 6.10.4).

Measure	Variable	Analysis Method (Sections 6.1 and 6.3)	Population (Section 6.1.1)	Comparison/Time Point	Analysis Type
		ANCOVA with mBOCF	ITT Population with Current or Historical Enthesitis at Baseline	IXE80Q2W & IXE80Q4W vs. placebo at Weeks 16 and 52 and all other postbaseline visits in Period 2	Other secondary efficacy analyses (Section 6.10.4).
	MASES score = 0 (similarly SPARCC = 0)	Logistic regression analysis with NRI; Fisher's exact test with NRI	ITT Population with Baseline MASES >0 (or SPARCC >0)	IXE80Q2W & IXE80Q4W vs. placebo at Weeks 16 and 52 and all other postbaseline visits in Period 2	Other secondary efficacy analyses (Section 6.10.4).
		Logistic regression analysis with NRI; Fisher's exact test with NRI	ITT Population with Current or Historical Enthesitis at Baseline	IXE80Q2W & IXE80Q4W vs. placebo at Weeks 16 and 52 and all other postbaseline visits in Period 2	Other secondary efficacy analyses (Section 6.10.4).
Peripheral Arthritis	TJC and SJC change from baseline	MMRM	ITT Population with baseline TJC >0 (or SJC >0)	IXE80Q2W & IXE80Q4W vs. placebo at Weeks 16 and 52 and all other postbaseline visits in Period 2	Other secondary efficacy analyses (Section 6.10.4).
		ANCOVA with mBOCF	ITT Population with baseline TJC >0 (or SJC>0)	IXE80Q2W & IXE80Q4W vs. placebo at Weeks 16 and 52 and all other postbaseline visits in Period 2	Other secondary efficacy analyses (Section 6.10.4).
		ANCOVA with mBOCF	ITT Population with Current or Historical Enthesitis at Baseline	IXE80Q2W & IXE80Q4W vs. placebo at Weeks 16 and 52 and all other postbaseline visits in Period 2	Other secondary efficacy analyses (Section 6.10.4).
	TJC = 0 when baseline TJC > 0 (similarly SJC = 0 when baseline SJC > 0)	Logistic regression analysis with NRI; Fisher's exact test with NRI	ITT Population with Baseline TJC>0 (or SJC>0)	IXE80Q2W & IXE80Q4W vs. placebo at Weeks 16 and 52 and all other postbaseline visits in Period 2	Other secondary efficacy analyses (Section 6.10.4).

Measure	Variable	Analysis Method (Sections 6.1 and 6.3)	Population (Section 6.1.1)	Comparison/Time Point	Analysis Type
	TJC = 0 when patients had current or historical peripheral arthritis at baseline (similarly SJC = 0 when patients had current or historical peripheral arthritis at baseline)	Logistic regression analysis with NRI; Fisher’s exact test with NRI	ITT Population with Current or Historical Peripheral Arthritis at Baseline	IXE80Q2W & IXE80Q4W vs. placebo at Week 16 and 52 and all other postbaseline visits in Period 2	Other secondary efficacy analyses (Section 6.10.4).
Anterior uveitis	Crude and exposure-adjusted incidence rates for patients with anterior uveitis	Fisher’s exact test and Poisson regression	ITT Population	IXE80Q2W & IXE80Q4W vs. placebo during Period 2	Other secondary efficacy analyses (Section 6.10.4).
NSAID (including COX-2 inhibitor) Intake	Proportion of patients taking NSAID (including COX-2 inhibitor)	Descriptive statistics	ITT Population	At Baseline (Week 0), Weeks 16, 20, 24, 28, 32, 36, 44, 52.	Analyses on NSAID intake (Section 6.10.4.1)
	Change from baseline in ASAS-NSAID	Descriptive statistics	ITT Population who have NSAID (including COX-2 inhibitor) intake at Baseline	At Weeks 16, 20, 24, 28, 32, 36, 44, 52.	Analyses on NSAID intake (Section 6.10.4.1)

Measure	Variable	Analysis Method (Sections 6.1 and 6.3)	Population (Section 6.1.1)	Comparison/Time Point	Analysis Type
	ASAS-NSAID50	Descriptive statistics	ITT Population who have NSAID (including COX-2 inhibitor) intake at Baseline	At Weeks 16, 20, 24, 28, 32, 36, 44, 52.	Analyses on NSAID intake (Section 6.10.4.1)

Abbreviations: ANCOVA = analysis of covariance; ASAS40 = Assessment of Spondyloarthritis International Society 40; ASDAS = Ankylosing Spondylitis Disease Activity Score; BASDAI50 = 50% of the Bath Ankylosing Spondylitis Disease Activity Index; BASFI = Bath Ankylosing Spondylitis Functional Index; BASMI = Bath Ankylosing Spondylitis Metrology Index; CRP = C-reactive protein; ITT = intent-to-treat; IXE80Q2W = ixekizumab 80 mg every 2 weeks; IXE80Q4W = ixekizumab 80 mg every 4 weeks; MASES = Maastricht Ankylosing Spondylitis Enthesitis Score; mBOCF = modified baseline observation carried forward; MMRM = mixed-effects model of repeated measures; NRI = nonresponder imputation; NSAID = non-steroidal anti-inflammatory drug; pMI = placebo multiple imputation; SJC = swollen joint count; SPARCC SIJ = Spondyloarthritis Research Consortium of Canada Score Sacroiliac Joint; TJC = tender joint count.

